Phase 1 Study Procedures	
A total of 12 patients will be randomly assigned to one of three groups, four patients per group, to receive a single intravenous injection of 5, 7, or 9 mCi of copper Cu 64 PSMA I&T.
 
Screening:
 
All patients will be screened to ensure they meet all inclusion and no exclusion criteria for enrollment in the study. Written informed consent will be obtained for all patients enrolled in the study.
 
Baseline Assessments:
 
Routine clinical chemistry, hematology, and urinalysis will be obtained for all patients prior to dosing. PSA will also be obtained for all patients prior to dosing.
 
Medical history and physical examination will be performed prior to dosing. This will include information on the history of the prostate cancer. Concomitant medication history will also be obtained.
 
A baseline 12-lead ECG will be obtained prior to dosing. Vital signs including heart rate, respiratory rate, and blood pressure will be assessed prior to dosing.
 
Randomization:
 
Patients will be randomized to receive a single dose of 5, 7 or 9 mCi of copper Cu 64 PSMA I&T injection.

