--	---

	
evaluations will be used in the determination of the injected dose value for the Phase 2 study.
 
Safety Assessments:
 
All patients will be followed for adverse events for 24 hours post-injection. Severity of adverse events will be assessed independently by the Investigators and graded using the National Cancer Institute Common Terminology Criteria for Adverse Events version 5.0, in which Grades 1, 2, 3, 4, and 5 describe adverse events as mild, moderate, severe, or medically significant but not life-threatening, life-threatening, and death related to adverse event, respectively.
 
Routine clinical chemistry, hematology, PSA, and urinalysis will be performed at 4 hours post-injection on all patients. If no clinically significant changes are noted, no additional follow-up will be performed. If significant findings are noted, they will be reassessed at 24 hours post-injection and followed until values return to normal or baseline, or until the Investigator and Medical Monitor determine it is no longer necessary.
 
A 12-lead ECG will be obtained at 30 minutes and 3.5 hours post-injection for all patients. If no clinically significant changes are noted, no additional follow-up will be performed. If significant findings are noted, the patient will be reassessed at 24 hours post-injection and followed until values return to normal or baseline, or until the Investigator and Medical Monitor determine it is no longer necessary.
 
Vital signs including heart rate, blood pressure, and respiratory rate will be obtained at 5 minutes, 30 minutes, 1 hour and 4 hours post-injection on all patients. If no clinically significant changes are noted, no additional follow-up will be performed. If significant findings are noted, they will be reassessed at 24 hours post-injection.
 
Follow-up:
 
Patients will be seen 24 hours post-injection for assessment of adverse events, clinically significant lab or ECG values or clinically significant vital signs. Patients with clinically significant changes will be followed until such events resolve or as decided by the Investigator and Medical Monitor.

--	--

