	
Baseline Assessments:
 
Routine clinical chemistry, hematology, and urinalysis will be obtained for all patients prior to dosing. PSA will also be obtained for all patients prior to dosing.
 
Medical history and physical examination will be performed prior to dosing. This will include information on the history of the prostate cancer. Concomitant medication history will also be obtained.
 
Imaging Procedure:
 
All patients will undergo PET/CT imaging at 1 hour <math>\pm</math> 15 minutes and 4 hours <math>\pm</math> 30 minutes following copper Cu 64 PSMA I&T injection using the dose determined in Phase 1. The 1 hour and 4-hour images will be independently read by three experienced blinded readers for the detection of prostate cancer. Specifically, each reader will categorize images as “Disease” or “No Disease” based only on tumor uptake of copper Cu 64 PSMA-I&T in each of the four regions: 1) prostate bed or prostate gland, 2) lymph nodes (pelvic and extra pelvic), 3) bone, and 4) viscera/soft tissue.
 
Efficacy Analysis:
 
Composite Reference Standard
 
All patients will undergo an efficacy assessment based on copper Cu 64 PSMA I&T PET/CT results and the results of clinical presentation for evaluation against the Composite Reference Standard.
 
The Composite Reference Standard is defined as follows:
 

1. Local histopathology obtained from prostate cancer surgery or biopsy obtained within 60 days before or following copper Cu 64 PSMA I&T PET/CT, or

2. If histopathology is not available, anatomical correlation of conventional image findings (e.g., targeted MRI or CT or any FDA-approved PET PSMA agent) that are acquired prior to locoregional or systemic treatment and within 60 days before or following copper Cu 64 PSMA I&T PET/CT

 
Safety Assessments:
 
All patients will be followed for adverse events for 24 hours post-injection. Severity of adverse events will be assessed independently by the Investigators and graded using the National Cancer Institute Common Terminology Criteria for Adverse Events version 5.0, in which Grades 1, 2, 3, 4, and 5 describe adverse events as mild, moderate, severe or medically significant but not life-threatening, life-threatening, and death related to the adverse event, respectively.

--	---

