	
Routine clinical chemistry, hematology, PSA, and urinalysis will be performed at 4 hours post-injection on all patients. If no clinically significant changes are noted, no additional follow-up will be performed. If significant findings are noted, they will be reassessed at 24 hours post-injection and followed until values return to normal or baseline, or until the Investigator and Medical Monitor determine it is no longer necessary.
 
A 12-lead ECG will be obtained at 30 minutes and 3.5 hours post-injection for all patients. If no clinically significant changes are noted, no additional follow-up will be performed. If significant findings are noted, the patient will be reassessed at 24 hours post-injection and followed until values return to normal or baseline, or until the Investigator and Medical Monitor determine it is no longer necessary.
 
Vital signs including heart rate, blood pressure, and respiratory rate will be obtained at 5 minutes, 30 minutes, 1-hour and 4-hour post-injection on all patients. If no clinically significant changes are noted, no additional follow-up will be performed. If significant findings are noted, they will be reassessed at 24 hours post-injection.
 
Follow-up:
 
Patients will be contacted 24 hours post-injection for assessment of adverse events, clinically significant lab or ECG values or clinically significant vital signs. Patients with clinically significant changes will be followed until such events resolve or as decided by the Investigator and Medical Monitor.
 
Patients will continue to be followed for disease progression by their physician per their standard of care. Any conventional imaging (dedicated CT, MRI, bone scan, or FDA-approved PET/CT) based on the site's clinical Standard of Care (SOC) performed within 12 months of administration may be collected to evaluate disease progression.

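### As listed in the synopsis, Phase 2 has no pre-dose ECG or vital signs, although Phase 1 requires both and the Phase 2 safety rules refer to changes and, for ECG, to baseline

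*Combined protocol and SAP*

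**What the plan says.** All references are to the Protocol Synopsis of the combined protocol and SAP.

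**Phase 1 Study Procedures, Baseline Assessments.** After laboratory tests, PSA, history, physical examination and medication history, a separate paragraph adds: "A baseline 12-lead ECG will be obtained prior to dosing" and "Vital signs including heart rate, respiratory rate, and blood pressure will be assessed prior to dosing".

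**Phase 2 Study Procedures, Baseline Assessments.** Laboratory tests and PSA are listed, then "Medical history and physical examination will be performed prior to dosing", with the prostate cancer history, and "Concomitant medication history will also be obtained". The list ends there and the imaging procedure follows.

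**Phase 2 Study Procedures, Safety Assessments.** For ECG: "A 12-lead ECG will be obtained at 30 minutes and 3.5 hours post-injection for all patients. If no clinically significant changes are noted", no further follow-up is done. Otherwise, "If significant findings are noted, the patient will be reassessed at 24 hours post-injection" and followed until values are normal or back at baseline, or until the Investigator and Medical Monitor decide to stop. For vital signs: "Vital signs including heart rate, blood pressure, and respiratory rate will be obtained at 5 minutes, 30 minutes, 1-hour and 4-hour post-injection", again with action depending on significant change, and reassessment at 24 hours if something is found.

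**Study Objectives, Phase 2.** Safety is the third primary objective. It names six measures: adverse events, clinical chemistry, hematology, urinalysis, ECG and vital signs.

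**The concern.** The Phase 2 safety rules speak of change and, for ECG, of return to baseline, but the listed procedures supply no starting value for either measure. Phase 2 gives every patient the same dose and has no control group, so a patient's own pre-dose reading is the only direct comparator.

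Without it, some abnormal post-injection results cannot be attributed with confidence. Shifts that stay within the normal range, for example in blood pressure or an ECG interval, cannot be measured from baseline at all. A pre-dose reading that was not taken cannot be recovered once the patient has been injected.

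**Working it through.** The plan states no figure that depends on this point, so the check is mainly a comparison of the two phases.

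**1. Baseline lists side by side**

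| Pre-dose item | Phase 1 | Phase 2 |
|---|---|---|
| Chemistry, hematology, urinalysis | listed | listed |
| PSA | listed | listed |
| Medical history, physical examination | listed | listed |
| Concomitant medication history | listed | listed |
| 12-lead ECG | listed | not listed |
| Heart rate, respiratory rate, blood pressure | listed | not listed |

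No other part of the Phase 2 procedures names a pre-dose ECG or vital sign. The Phase 2 list reads continuously, with no redaction or missing figure at this place.

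**2. Post-injection times in Phase 2**

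- ECG: 30 minutes and 3.5 hours, so 2 readings after injection and 0 before.
- Vital signs: 5 minutes, 30 minutes, 1 hour and 4 hours, so 4 readings after injection and 0 before.

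**3. Wording carried over from Phase 1.** The Phase 1 Safety Assessments use the same ECG sentence, "A 12-lead ECG will be obtained at 30 minutes and 3.5 hours post-injection for all patients", and nearly the same follow-up rules. There the reference to baseline is sound because a baseline was taken.

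**4. Patients with a pre-dose reference**

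- As listed: 0 of 26 in Phase 2, and 12 of 12 + 26 = 38 overall.
- With the fix: 26 of 26, and 38 of 38.

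**5. What can still be learned without a baseline**

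- All post-injection results normal: the patient is informative about new abnormalities.
- Abnormality appears or resolves across readings: the pattern says something about its cause.
- Abnormality known from the history: it can be recognised as old.
- Abnormality present at every reading and not in the history: it cannot be classed. A change that began before the first ECG at 30 minutes and persisted would look the same as one that was there all along.

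**6. Illustration only.** The documents do not say how many patients will enter with an ECG or vital-sign abnormality. If the proportion p were 5%, 10% or 20% (assumed), the expected number among 26 is 26p = 1.3, 2.6 or 5.2. The chance of at least one is 1 − (1 − p)^26 = 73.6%, 93.5% or 99.7%. History and serial readings would settle some of these cases, so these are not counts of unclassifiable patients.

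**The case against.** **The full schedule may contain the measurements.** The available text is the abbreviations list and the synopsis. Wording that presupposes a baseline, copied almost unchanged from Phase 1, points at least as much to a dropped sentence as to a decision not to measure. This stands. A reader might infer that the sponsor chose to omit baseline readings, or that change from baseline will certainly be impossible. The documents support neither, so the conclusion is conditional on running Phase 2 as listed.

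**The physical examination covers vital signs.** This does not stand. Phase 1 lists the examination and vital signs separately, and an examination yields no 12-lead ECG.

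**No planned analysis is lost.** This stands in part. The synopsis specifies no change-from-baseline summary for these measures, no rate of new abnormalities, no confidence limit, and no pooling of the phases at one dose. The harm is to interpretation, though the plan's own references to change and baseline still need a reference value.

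**Ambiguous cases need not bias a rate.** This stands. A reader might infer that each must be either counted as new or put down to prior disease. In fact, onset can be reported as undetermined.

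A reader might also infer a large effect on an upper safety limit. Pooling 4 + 26 = 30 patients, with three pre-existing cases and no new ones, the exact one-sided 95% limit (the 0.95 quantile of a beta distribution with parameters x + 1 and n − x) is 10.5% for 0 of 27 if they are set aside, and 23.9% for 3 of 30 if all are counted as new. The arithmetic is right, but it needs an assumed prevalence of about 10%, a worst-case counting rule and a pooled analysis that the plan does not specify. If two of the three were settled and set aside, 1 of 28 gives about 16%. With no abnormal result at all, the limit is 9.5% (0 of 30) with or without a baseline. These figures do not measure the effect of the omission.

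**Conclusion.** The point holds in conditional form. If Phase 2 is run as the synopsis lists it, none of its 26 patients has a reference reading for two of the six measures named in a primary safety objective. Two consequences follow without any assumption about prevalence: a persistent abnormality not known from the history cannot be classed as pre-existing or new, and shifts from baseline in ECG and vital signs cannot be measured.

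How many patients would be affected by the first cannot be derived from the documents. It may be none.

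The scope is narrow. Laboratory tests have a pre-dose value in Phase 2, and CLR, CDR and the sample size do not depend on these readings. The follow-up rule can still be operated, because it also allows return to normal values or a decision by the Investigator and Medical Monitor. The change should be made, given how little it costs. Confidence is medium, because a fuller schedule of assessments may already contain these measurements.

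**What to change.** Add the two Phase 1 sentences to the Phase 2 Baseline Assessments: a 12-lead ECG before dosing, and heart rate, respiratory rate and blood pressure before dosing. Align any fuller schedule of assessments and the eCRF. If that schedule already requires these measurements, correct the synopsis only.

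Each post-injection abnormality can then be compared with the patient's own pre-dose reading, and change from baseline can be reported for all 26 patients.

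The cost is protocol and eCRF wording and a few minutes per patient before injection. The equipment and staff are already needed for vital signs at 5 minutes and the ECG at 30 minutes after injection.

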## PROTOCOL SYNOPSIS

Title of Study	A Multi-Center, Open-Label, Randomized Phase 1/2 Study of Copper Cu 64 PSMA I&T Injection in Patients with Histologically Proven Metastatic Prostate Cancer
Phase of Clinical Trial	Phase 1/2
Indication	Detection and localization of recurrent prostate cancer in men with biochemical recurrence based on elevated blood prostate specific antigen (PSA) levels following prior treatment.
Number of Sites	5-10
Drug Product	Copper Cu 64 PSMA I&T
Study Objectives	
Phase 1
 
Primary Objectives:
 
The primary objectives of the Phase 1 portion of this study are:
 

1. To assess the safety and determine radiation dosimetry estimates following intravenous administration of 5, 7, and 9 mCi doses of copper Cu 64 PSMA I&T injection in patients with recurrent prostate cancer. Safety will be assessed by monitoring adverse events, clinical chemistry, hematology, urinalysis, vital signs, ECG, and determination of radiation absorbed dose estimates.

2. To assess the PET/CT image quality following intravenous administration of 5, 7, and 9 mCi doses of copper Cu 64 PSMA I&T injection to determine an acceptable dose for obtaining diagnostic quality PET/CT images.

 
Phase 2
 
Primary Objectives:
 
The primary objectives of the Phase 2 portion of this study are:
 

1. To determine the region-level correct localization rate (CLR) of copper Cu 64 PSMA I&T injection PET/CT imaging for the detection of recurrent metastatic prostate cancer at 1 hour and 4 hours post injection. The CLR is defined as the percentage of regions containing at least one true PET positive lesion, with exactly localized correspondence between PET/CT imaging and the Composite Reference Standard regardless of any co-existent false positive findings, within the same region, out of all regions containing at least one PET positive finding.

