	
2. To determine the patient-level correct detection rate (CDR) of copper Cu 64 PSMA I&T injection PET/CT imaging for the detection of recurrent metastatic prostate cancer at 1 hour and 4 hours post injection. The CDR is defined as the percentage of patients who have at least one true PET positive lesion, with exactly localized correspondence between PET imaging and the Composite Reference Standard, regardless of any co-existent false positive findings, out of all patients who are scanned.
 
3. To assess the safety of copper Cu 64 PSMA I&T injection in patients with recurrent prostate cancer. Safety will be assessed by monitoring adverse events, clinical chemistry, hematology, urinalysis, ECG, and vital signs.
 
Secondary Objective:
 
1. To compare the diagnostic quality of PET/CT images obtained at 1 hour and 4 hours post copper Cu 64 PSMA I&T injection.

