Study Design	
This is a prospective, open-label Phase 1/2 study to evaluate copper Cu 64 PSMA I&T injection for PET/CT imaging in patients with recurrent metastatic prostate cancer after radical prostatectomy or radiation therapy.
 
Phase 1
 
The Phase 1 portion of the study will include a total of 12 patients with metastatic prostate cancer. Patients will be randomized into three groups of four patients. Patients in each group will receive a single intravenous dose of 5, 7, or 9 mCi of copper Cu 64 PSMA I&T. Whole-body PET/CT images will be acquired at 1 hour <math>\pm</math> 15 minutes, 4 hours <math>\pm</math> 0.5 hours, and 24 hours <math>\pm</math> 2.0 hours post-injection to determine radiation absorbed dose estimates.
 
The 1 hour and 4-hour PET/CT images will be evaluated independently by three readers blinded to all patient information and dose administered to assess the quality of the images (24 PET/CT image sets total). The assessments will be used to determine an acceptable dose to be administered for the Phase 2 study.
 
Phase 2
 
The Phase 2 portion of the study will include a separate group of 26 patients with metastatic prostate cancer. Each patient will be administered the same intravenous dose of copper Cu 64 PSMA I&T injection determined in the Phase 1 study. PET/CT images will be acquired for all patients at 1 hour <math>\pm</math> 15 minutes and 4 hours <math>\pm</math> 30 minutes post copper Cu 64 PSMA I&T injection.
 
The PET/CT images will be interpreted independently by three readers blinded to all patient information. Each patient study will be assessed and scored for the detection of prostate cancer. Specifically, each reader will categorize images as "Disease" or "No Disease" based only on tumor

	
uptake of copper Cu 64 PSMA-I&T in each of the four regions: 1) prostate bed or prostate gland, 2) lymph nodes (pelvic and extra pelvic), 3) bone, and 4) viscera/soft tissue. Analysis of the reads will be used for determination of the CLR and CDR for 1 hour and 4-hour post-injection imaging of copper Cu 64 PSMA I&T PET/CT by comparison to the Composite Reference Standard.

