	
1. To determine the region-level correct localization rate (CLR) of copper Cu 64 PSMA I&T injection PET/CT imaging for the detection of recurrent metastatic prostate cancer at 1- and 4-hours post-injection. The CLR is defined as the percentage of regions containing at least one true PET positive lesion, with exactly localized correspondence between PET/CT imaging and the Composite Reference Standard regardless of any co-existent false positive findings, within the same region, out of all regions containing at least one PET positive finding.
 
2. To determine the patient-level correct detection rate (CDR) of copper Cu 64 PSMA I&T injection PET/CT imaging for the detection of recurrent metastatic prostate cancer at 1 hour and 4 hours post-injection. The CDR is defined as the percentage of patients who have a least one true PET positive lesion with exactly localized correspondence between PET imaging and the Composite Reference Standard regardless of any co-existent false positive findings, out of all patients who are scanned
 
Since all patients enrolled in the study will have disease, the CLR is a measure of the sensitivity of the copper Cu 64 PSMA I&T injection scan. Current methods have a CLR of 60%; thus, the hypothesis to be tested in the Phase 2 portion of the study is: H0: <math>\pi_C = \pi_0</math> versus HA: <math>\pi_C > \pi_0</math> where <math>\pi_C</math> is the CLR for copper Cu 64 PSMA I&T injection and <math>\pi_0</math> is the CLR from the literature (estimated to be 60%).
 
This hypothesis will be tested using an exact one-sample binomial test with a one-sided <math>\alpha=0.025</math>.
 
Secondary Objective:
 
The secondary objective for the Phase 2 study is to compare the diagnostic quality of PET/CT images obtained at 1 hour and 4 hours post copper Cu 64 PSMA I&T injection.
 
Safety Endpoint:
 
To assess the safety of copper Cu 64 PSMA I&T injection in patients with recurrent prostate cancer. Safety will be assessed by monitoring adverse events, clinical chemistry, hematology, urinalysis, ECG, and vital signs.
 
Analysis Populations:
 
Several analysis populations of patients are defined, which may provide a more complete description of the collected data, provide a logical mechanism for grouping and listing results based on an applied analysis, and/or allow appropriate stratification of various analyses.
 
1. The Enrolled Patient Population (EPP) represents patients who sign an Informed Consent Form and have baseline data.

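### Does the single one-sided 0.025 CLR test need a stated time point and reader rule, given two time points and three readers?

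*Combined protocol and SAP*

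**What the plan says.** In the Protocol Synopsis, the first Phase 2 primary objective is the region-level CLR "for the detection of recurrent metastatic prostate cancer at 1 hour and 4 hours post injection". The Statistical Analysis row repeats it as a primary efficacy endpoint "for the detection of recurrent metastatic prostate cancer at 1- and 4-hours post-injection". The Study Design row confirms two sets of results: "Analysis of the reads will be used for determination of the CLR and CDR for 1 hour and 4-hour post-injection imaging".

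The Phase 2 Imaging Procedure says that the 1-hour and 4-hour "images will be independently read by three experienced blinded readers", with disease scored "in each of the four regions: 1) prostate bed or prostate gland" and in lymph nodes, bone, and viscera or soft tissue.

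The inferential statement is singular: "thus, the hypothesis to be tested in the Phase 2 portion of the study is" that the CLR exceeds a literature value of 60%. "This hypothesis will be tested using an exact one-sample binomial test with a one-sided" level of 0.025. The CLR symbol carries no index for time or reader.

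The secondary objective does not favour either time point: "To compare the diagnostic quality of PET/CT images obtained at 1 hour and 4 hours post copper Cu 64 PSMA" I&T injection. The patient-level correct detection rate (CDR) is also primary at both times, but no hypothesis is attached to it.

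**The concern.** Two time points and three readers give 2 × 3 = 6 CLR results, while the plan describes one test. The synopsis does not say which time point carries it, whether one or both must succeed, or how the readers combine. Two analysts could therefore take the same data and reach different answers on the primary CLR objective, each consistent with the text. If the rule were chosen once the reads were known, the false-positive rate of the only formal Phase 2 test could exceed its nominal 0.025.

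**Working it through.** **Inputs from the synopsis.** Null CLR 60%; exact one-sample binomial test, one-sided 0.025; two time points; three readers; 26 patients; four regions per patient, so at most 26 × 4 = 104 positive regions per read. It gives no alternative CLR, power or expected number of positive regions, so there is no sample-size figure to reproduce.

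**Assumptions.** 26 or 60 positive regions, independent, with the same count in every read. Latent-normal correlation between time points is 0.5 to 0.85 for one reader. For six reads, the (time, reader) correlations are (0.5, 0.5), (0.8, 0.7) and (0.9, 0.8). The true CLR is 60% throughout.

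**Step 1: one test.** The cut-off is the smallest r with P(X ≥ r | n, 0.60) ≤ 0.025.
- n = 26: r = 21, size a = 0.0214.
- n = 60: r = 44, size a = 0.0221.

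**Step 2: one reader, either time point counts.** Error = 2a − b, where b is the probability that both reject. At n = 26 and correlation 0.5, b = 0.0020, so 2 × 0.0214 − 0.0020 = 0.0408.

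| Positive regions | corr. 0.5 | corr. 0.7 | corr. 0.85 |
|---|---|---|---|
| 26 | 0.0408 | 0.0392 | 0.0370 |
| 50 | 0.0255 | 0.0247 | 0.0234 |
| 60 | 0.0420 | 0.0404 | 0.0381 |

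The dip at 50 arises because the exact test is conservative there (size 0.0133). Whatever the correlation, error cannot exceed 2 × 0.025 = 0.05.

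**Step 3: both time points required.** If both true CLRs are 60%, error is b, at most 0.007 over these correlations. If one true CLR is above 60%, error is still bounded by the single-test size, 0.0214 or 0.0221.

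**Step 4: three readers, n = 26.**

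| Rule | (0.5, 0.5) | (0.8, 0.7) | (0.9, 0.8) |
|---|---|---|---|
| Any of six results | 0.108 | 0.093 | 0.081 |
| Two of three readers, at either time point | 0.010 | 0.015 | 0.017 |
| Two of three readers, at one named time point | 0.006 | 0.008 | 0.010 |

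If the six reads were independent, any-of-six would give 1 − (1 − 0.0214)^6 = 0.122. Over 26 to 60 independent regions, the two-of-three rule at either time point gives 0.005 to 0.020.

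**Step 5: set against the text.** The rules that exceed 0.025 all require a win at either time point by one reader, a win in any of the six results, or some improper pooling of reads. The synopsis states none of these. It states one hypothesis and one test. Read literally, that is one claim at 0.025, with the choice of result left to be specified.

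**The case for a change.** The strongest case for a change is that this is the only formal test in Phase 2, the synopsis already gives its hypothesis, method and level, and the missing index is a gap within that statement. A sentence would close it at no cost in patients or reads. Some ways of filling it would do harm. Any-of-six gives roughly 0.08 to 0.11. Treating three readers' reads of 26 regions as 78 independent observations (cut-off 56 of 78) gives about 0.057 to 0.098 for reader correlation 0.5 to 0.9.

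Part of this stands. The rule is not in the synopsis, and it must be settled before the Phase 2 reads are analysed. It does not follow that the plan is wrong. Naming one time point, testing in sequence and requiring both are all defensible and all hold 0.025 for a single reader result. Choosing among them trades power against breadth of claim. At an assumed CLR of 80%, correlation 0.7 and 60 independent regions, two-of-three power is 0.95 at the first time point and 0.92 if both are required. At 26 regions the figures are 0.59 and 0.46. The objective can also be read as estimating two rates, each reported separately in a small Phase 1/2 study. A synopsis is not the usual place for reader-combination rules, and the text available here ends with its analysis populations.

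Two arguments for a larger effect do not hold up. The number of positive regions is not confined to 26 to 104, because a patient with no positive finding contributes none, so a tally of how many counts in that range exceed 0.025 means little. And the higher error rates seen when regions cluster within patients (0.068 to 0.076 for one reader at either time point, with three regions per patient and within-patient correlation 0.3) start from 0.041 with a single reader and a single time point. That excess comes from the independence assumption of the binomial test. It is a separate matter from multiplicity.

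**Conclusion.** This is a gap that analysts can fill sensibly, and no change to the plan follows. Across the two time points, error for a single reader result is at most 0.05 under the most permissive reading (about 0.037 to 0.042 at 26 or 60 regions) and at most 0.025 if one time point is named or both are required. Requiring two of three readers keeps it at 0.005 to 0.020 with 26 to 60 independent regions, even when either time point counts. The figures of 0.08 to 0.11 need an any-of-six rule that the plan does not state. These results rest on assumed region counts, equal counts across reads, independent regions and the assumed correlations; the two-of-three result in particular is not a bound for every correlation. The conclusion also assumes that the time point and reader rule are settled before the reads are known, as is ordinary practice in a detailed analysis specification.
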